3.2 Treatment Groups and Duration

All subjects will receive tapinarof cream, 1% QD for 27 days, at an appropriate dose in accordance with the size of the affected area. Subjects or their caregivers will be instructed to apply a thin layer to the affected areas.

3.3 Definition of Study Completion and Eligibility for Long-Term Extension Study

In order to complete the study, a subject must complete 4 weeks of assessments. To be considered a “study completer” in terms of treatment period, a subject must complete $\geq 80.0\%$ of the intended doses. The number of intended doses is defined as the study day of the subject’s Day 28 visit minus 1 (e.g., if the subject’s Day 28 visit occurs exactly on Day 28 then their number of intended doses is 27).

To be eligible for the open-label, long-term safety study, subjects must be a “study completer”. Subjects who complete the study will have the option to enroll into the Phase 3 open-label long term safety study of 48 weeks in duration. Details of that study are provided in a separate clinical trial protocol.

The end of the study is defined as when the last subject has completed the 4 weeks of assessments and either enrolls in the long-term safety study or does not enroll and completes the Follow-up visit.

4 Study Population

4.1 Type and Number of Subjects

Approximately 36 subjects ages 2 to 17 years old will be enrolled in the study with approximately 12 subjects, and a minimum of 10 subjects, enrolled into each of the three following age cohorts: 2-6 years old, 7-11 years old, 12-17 years old. Subjects across the age range will be enrolled simultaneously.

Protocol violations from inclusion and exclusion criteria are prohibited because ineligible study subjects can potentially jeopardize the scientific integrity of the study, regulatory acceptability, or subject safety. Therefore, adherence to the criteria as specified in the protocol is essential.

4.2 Inclusion Criteria

Each subject must meet all of the following criteria to be eligible to participate in the study:

1. Male and female subjects ages 2 to 17 years with a clinical diagnosis of AD by Hanifin and Rajka criteria [[Hanifin, 1980](#)] (see [Appendix 1](#)).
2. Subjects with AD covering $\geq 25\%$ of the BSA for subjects ages 12-17 years old, or $\geq 35\%$ of the BSA for subjects ages 2-11 years old, suitable for topical therapy. Scalp should be excluded from the BSA calculation to determine eligibility during Screening and at Baseline, and for all efficacy assessments.
3. A vIGA-AD™ score of 3 or greater at Screening and Baseline (pre-dosing).
4. AD present for at least 6 months for subjects ages 6-17 years old or 3 months for subjects ages 2 to 5 years old, confirmed by prior medical documentation and/or according to the subject and/or caregiver(s).
5. Female subjects of childbearing potential who are engaging in sexual activity that could lead to pregnancy should use one of the following acceptable birth control methods while on study and for 4 weeks after the last exposure to study drug.
 - Acceptable contraception methods include intrauterine device, hormonal contraceptives, barrier method (e.g., condom or diaphragm), or surgical sterilization of male partner (vasectomy)
 - Subjects who claim abstinence as their method of contraception are allowed provided they agree to use a barrier method (e.g., condom or diaphragm) should they become sexually active from Screening to 4 weeks after the last dose of study drug
 - Non-child-bearing potential is defined as:
 - premenarchal
 - pre-menopausal females with a documented bilateral tubal ligation, bilateral oophorectomy, hysterectomy, or hysteroscopic sterilization
6. Female subjects of childbearing potential must have a negative serum pregnancy test at Screening and a negative urine pregnancy test at Baseline (Day 1).
7. Subject, subject's parent(s), or legal representative must be capable of giving written informed consent, which includes compliance with the requirements and restrictions listed in the consent/assent form; written informed consent must be obtained prior to any study related procedures.

4.3 Exclusion Criteria

A subject who meets any of the following criteria will be excluded and considered ineligible for participation in the study:

1. Concurrent conditions:
 - a. Immunocompromised (e.g., lymphoma, acquired immunodeficiency syndrome) or medical history of positive human immunodeficiency virus antibody at Screening.
 - b. Chronic or acute systemic infection requiring treatment with antiparasitics, or antiprotozoals, within 4 weeks prior to the Baseline visit.
 - c. Chronic or acute systemic bacterial infection requiring treatment with systemic antibiotics within one week prior to the Baseline visit.
 - d. Chronic or acute superficial fungal infection requiring treatment with systemic antifungals within one week prior to the Baseline visit
 - e. Acute active bacterial, fungal, or viral (herpes simplex, herpes zoster, chicken pox) skin infection within one week prior to the Baseline visit; the condition should be completely resolved one week prior to Baseline Visit
 - f. Significant dermatologic or inflammatory condition other than AD that, in the Investigator's opinion, would make it difficult to interpret data or assessments during the study. For example, subjects with an active skin condition such as Kaposi's varicelliform eruption, scabies, molluscum contagiosum, impetigo, psoriasis, severe acne, connective tissue disorder, or Netherton's syndrome, or any other concurrent active disease.
 - g. Concurrent skin lesions in the treatment area or pruritus due to conditions other than AD that, in the opinion of the Investigator, would either interfere with study evaluations or affect the safety of the subject.
2. Screening alanine aminotransferase (ALT) or aspartate aminotransferase (AST) $\geq 2.0 \times$ the upper limit of normal (ULN).
3. Screening total bilirubin $> 1.5 \times$ ULN; total bilirubin $> 1.5 \times$ ULN is acceptable if bilirubin is fractionated and direct bilirubin $< 35\%$.
4. Current or chronic history of liver disease, known hepatic or biliary abnormalities (with the exception of Gilbert's syndrome or asymptomatic gallstones), presence of hepatitis B surface antigen (HBsAg), or positive hepatitis C antibody test result, or presence of anti-hepatitis B core antigen (anti-HBc). Subjects having a negative HBsAg and a positive anti-HBc may enroll if they have a positive anti-hepatitis B surface antigen demonstrating natural immunity. Subjects with a history of hepatitis C virus infection who were medically cured and have an undetectable viral load are eligible to enroll. Subjects with a history of stable non-alcoholic fatty liver disease without evidence of active inflammation (elevated ALT/AST $\geq 2.0 \times$ ULN) or cirrhosis are eligible to enroll.

5. Current or a history of cancer within 5 years except for adequately treated skin basal cell carcinoma, cutaneous squamous cell carcinoma or carcinoma in situ of the cervix (surgical excision or electrodesiccation and curettage).
6. Subjects who would not be considered suitable for topical therapy (e.g., those with extensive disease involvement over a large BSA who would be candidates for systemic therapy).
7. Use of any prohibited medication or procedure within the indicated period before the Baseline visit.

NOTE: Prohibited concomitant medications, therapy, etc. during the defined period are as listed in the bullets below. If a subject requires any of these medications throughout the study period, he/she may be excluded from or discontinued from the study, at the discretion of the Investigator and Medical Monitor.

- a. From 4 months prior to Baseline until the completion of the Follow-up visit or study discontinuation:
 - DUPIXENT® (dupilumab) injection.
 - Any monoclonal antibody product that becomes approved for AD during the course of the trial.
- b. From 28 days prior to Baseline until the completion of the Follow-up visit or discontinuation:
 - Oral, injectable, and suppository preparations of corticosteroids. Eye drops and nasal preparations are allowed. Inhaled preparations are allowed when used for a stable condition and stable dose for \geq 28 days before Screening and are continued at the same dose throughout the study.
 - Oral preparations and injections of immunosuppressants (cyclosporine, methotrexate, azathioprine, tacrolimus, Janus kinase inhibitors, etc.).
 - Excessive sun exposure, tanning booth, other ultraviolet light source and phototherapy including psoralen and ultraviolet A therapy or is unwilling to minimize natural and artificial sunlight exposure.
 - Treatment with antivirals with the exception of short-term treatment for acute upper respiratory viral infections (i.e., influenza) or viral suppressive therapy for a history of recurrent herpes labialis or genital herpes.
- c. From 14 days prior to Baseline until the completion of the Follow-up visit or discontinuation:
 - EUCRISA® (crisaborole) and any other PDE4 inhibitor.
 - Tacrolimus ointment and pimecrolimus cream.
 - Topical corticosteroids that are classified as medium or high potency (e.g., fluocinonide, triamcinolone acetonide) or super-high potency (e.g., clobetasol propionate). Eye drops and nasal preparations are allowed.

- Coal tar products (on the body). If subject chooses to treat scalp with study drug, then coal tar products are prohibited for use on the scalp.
- Over the counter or herbal medicines for atopic dermatitis (topical and oral preparations). If subjects are using emollients, they may continue to use the same emollient on nonlesional skin during the study. Emollients containing salicylic acid are prohibited during the study.

d. From 7 days prior to Baseline until the completion of the Follow-up visit or discontinuation:

- Topical corticosteroids that are classified as low potency (e.g., desonide, hydrocortisone).
- Oral, injectable, or intravenous antibiotics or antifungal medications.
- Topical doxepin, topical gentamicin, or topical neomycin sulfate.

NOTE: Oral doxepin is allowed for treatment of depression if subject has been on a stable dose (4 weeks) at Screening.

- Topical products containing urea, except for the treatment of follicular events
- Antihistamines/antiallergics (oral, topical and injections): diphenhydramine, chlorpheniramine maleate, hydroxyzine.

NOTE: The following antihistamines are allowed from Screening throughout the treatment period: loratadine, fexofenadine hydrochloride, cetirizine hydrochloride. Subjects are allowed to switch from non-allowed antihistamines during Screening but must be on a stable dose for 7 days prior to Baseline.

e. The subject has received an investigational product within the following time period prior to the first dosing day in the current study: 30 days or 5 half-lives of the investigational product (whichever is longer).

8. A history of or ongoing serious illness or medical, physical, or psychiatric condition(s) that, in the Investigator's opinion, may interfere with the subject's participation in the study, interpretation of results, or ability to understand and give informed consent.
9. Pregnant females as determined by positive serum (Screening) or urine (Baseline) human chorionic gonadotropin test.
10. Lactating females.
11. History of sensitivity to the study medications, or components thereof or a history of drug or other allergy that, in the opinion of the Investigator or Medical Monitor, contraindicates their participation.
12. Previous known participation in a clinical study with tapinarof (previously known as GSK2894512 and WBI-1001).

4.4 Lifestyle Restrictions

Subjects must avoid ultraviolet light, phototherapy, and excessive sun exposure throughout the study. When prolonged exposure cannot be avoided, use of sunscreen products (except on AD lesions) and protective apparel are recommended.

4.5 Screening/Baseline Failures

To determine subject eligibility at Screening and Baseline, a single repeat of tests or procedures may be allowed during the screening period at the discretion of the Investigator; the Medical Monitor should be consulted if needed.

Screen failures are defined as subjects who consent to participate in the clinical study but are not subsequently enrolled. A minimal set of screen failure information is required to ensure transparent reporting of screen failure subjects to meet the Consolidated Standards of Reporting Trials publishing requirements and to respond to queries from regulatory authorities. Minimal information includes demography, screen failure details, eligibility criteria, and any AEs/SAEs.

A subject who screen fails may be allowed to re-screen one time at the discretion of the Investigator; the Medical Monitor should be consulted, if needed.

4.6 Withdrawal Criteria

A subject may voluntarily discontinue treatment and/or withdraw from participation in this study at any time at his/her own request or may be discontinued from study treatment at any time at the discretion of the Investigator for safety, behavioral, compliance, or administrative reasons. Subjects withdrawn from the study will not be replaced.

4.6.1 Reasons for Withdrawal from the Study

Study drug will be discontinued and the subject will be withdrawn from the study for any of the following reasons:

- Subject has an AE that is considered to be related to study drug or procedures AND is severe enough to warrant treatment discontinuation, as determined by the Investigator (Section 8.1).
- Pregnancy
- Any Grade 3 or 4 AE, based on National Cancer Institute Common Terminology Criteria for Adverse Events (CTCAE) criteria, considered causally related to study drug (Section 8.2.2)

Study drug may be discontinued and the subject withdrawn from the study for any of the following reasons:

- Subject requires concurrent prohibited medication during the study. Nonmedicated emollients that do not contain salicylic acid may be used on nonlesional skin; emollients should not be applied to lesional skin during treatment. The same emollient should be used throughout the subject's participation in the study.

NOTE: If, in the opinion of the Investigator and the study Medical Monitor, such medication will not interfere with the conduct or interpretation of the study or compromise the safety of the subject, then the subject may continue to receive study drug. If the subject is permanently discontinued from study drug, they may remain in the study for safety assessments as needed, at the discretion of the Investigator and Medical Monitor, but they are not eligible to enroll in the open-label, long-term safety study.

- Subject noncompliance

- Investigator noncompliance
- Discontinuation of the study at the request of the Sponsor, regulatory agency, or an Institutional Review Board (IRB)/Independent Ethics Committee (IEC).

If a subject meets a withdrawal criterion during treatment, an Early Termination visit will be required (Section 7.7).

4.6.2 Withdrawal Procedures

The primary reason for the discontinuation of study drug and/or withdrawal from study must be recorded in the source document and on the case report form (CRF). If a subject is prematurely discontinued from study drug, the Investigator must make every effort to perform an Early Termination Visit (Section 7.7) and document the primary reason for withdrawal.

4.7 Lost to Follow-Up

A subject is considered lost to follow-up if he/she repeatedly fails to return to the study site for scheduled visits and is unable to be contacted by the study site. The following actions must be taken if a subject fails to return to the clinic for a required study visit:

- The site must attempt to contact the subject and/or caregiver(s) and reschedule the missed visit as soon as possible, counsel the subject on the importance of maintaining the assigned visit schedule, and ascertain whether or not the subject wishes to and/or should continue in the study.
- Before a subject is deemed lost to follow-up, the Investigator or designee must make every effort to regain contact with the subject and/or caregiver(s) (where possible, 3 telephone calls and, if necessary, a certified letter to the subject's last known mailing address or local equivalent methods). These contact attempts should be documented in the subject's medical record.
- Should the subject and/or caregiver(s) continue to be unreachable, he/she will be considered to have withdrawn from the study with a primary reason of lost to follow-up. In this case, the discontinuation date will be listed as the date the certified letter was mailed to the subject.

5 Study Treatment

5.1 Study Drug

5.1.1 Description, Packaging, and Labeling

The description of the study drug, tapinarof cream, 1%, is presented in Table 2.

Table 2: Tapinarof Cream

[REDACTED]	[REDACTED]

[REDACTED]

All labels for tapinarof cream, 1% to be distributed in the participating countries will meet all applicable requirements of those countries.

5.1.2 Storage

All study drug must be stored in a secure, environmentally controlled and monitored (manual or automated) area in accordance with the labeled storage conditions, with access limited to the Investigator and authorized site staff. The study drug storage temperature range will be provided in the study reference manual.

5.1.3 Handling and Disposal

Under normal conditions of handling and administration, study drug is not expected to pose significant safety risks to site staff. In the case of unintentional occupational exposure notify the monitor, Medical Monitor and/or the Sponsor study contact.

Arrangements will be made for used and unused drug supplies to be returned to the Sponsor or Sponsor designee, or for destruction on site following acceptable, documented procedures. Further guidance and information for final disposition of unused study drug will be provided.

5.1.4 Preparation

No special preparation of study drug is required.

5.1.5 Administration of Study Drug

Study drug will be dispensed to subjects and/or their caregivers at the clinical site in appropriately labeled tubes.

Subjects and/or caregivers will take the tubes home and self-administer study drug (or have caregiver(s) apply if necessary) to affected areas QD, except on clinic visit days when study drug is applied under supervision at the site.

Subjects will be instructed to apply study drug as follows:

- QD application to affected areas; subjects or their caregivers are advised to choose the application time they prefer and to apply the study drug at that approximate time each day of study participation. Subjects should avoid dosing around midnight to avoid potentially dosing twice in one calendar day.
- If a subject misses a daily dose, it will be recorded as a protocol deviation. The subject should continue dosing the next day and should not apply more than QD to make up for the missed dose on the previous day. If a dose is missed, the missed dose and the reason for the missed dose should be recorded in the daily diary as such. Itch rating can still be recorded in the diary even if a daily dose was missed
- On Day 1, study drug application should be avoided at the site of phlebotomy for PK blood draws.
- Study drug should be applied to dry, clean skin.
- Study drug may be applied to skin around the eye but avoid direct contact with the eye – study drug is not for ophthalmic use.
- Wash hands after application, unless treating lesions on the hands.
- Study drug should be applied to all lesions, including newly appearing lesions and lesions that have improved during the study. A body diagram identifying locations of lesions may be provided to the subject and/or caregiver.
- Subjects are allowed, but not required, to treat scalp lesions with study drug; however, efficacy analyses will not include assessment of AD in this area.
- If there is residual cream visible on the disease-affected lesional skin, then the subject and/or caregiver should be instructed to continue to lightly rub the cream into the skin until it is no longer visible.
- If study drug is applied to the subject by another person, that person should thoroughly wash his/her hands after application.
- When dosing at home, subjects and/or caregivers should record the time of study drug application in the daily diary. Itch rating should also be recorded in the diary.
- Nonmedicated emollients that do not contain salicylic acid may be used on nonlesional skin but the subject (or caregiver) should wait at least 30 minutes after applying study drug before applying nonmedicated emollients; emollients should not be applied to lesional skin during treatment. The same emollient should be used throughout the subject's participation in the study.
- On clinic visit days, study drug should be applied in the clinic under the supervision of site personnel.

NOTE: The time of the dose and assessments on clinic visit days will depend on the time of the clinic visit. Therefore, the timing of the clinic visit may differ from the subject's chosen dosing time. The intention is to allow flexibility to accommodate subjects' schedules.

Subjects and/or caregivers will be instructed/reminded on how to apply study drug at each clinic visit (except during the final treatment visit).

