- c. Physical examination will include height and weight, (BMI will be calculated in the CRF); a brief physical examination will be performed at other visits.
- d. Medical history will include month and year of AD diagnosis. As part of the subject's medical history, all systemic (oral and injectable) medications used by the subject for treatment of AD prior to 30 days before the Screening visit will be collected.
- e. Record any changes to medical history and document changes in source and EDC.
- f. Serum pregnancy test to be performed at the Screening visit only and urine pregnancy test to be performed at subsequent clinic visits when pregnancy testing is being performed.
- g. Urine pregnancy test to be performed before dosing.
- h. Clinical laboratory assessments include serum chemistry and liver chemistry tests, and hematology.
- i. If needed for ongoing AE or laboratory abnormality from previous visit.
- j. Vital signs will include systolic and diastolic blood pressure, pulse rate, and body temperature and should be measured after the subject is seated for at least 5 minutes. Vital signs will be measured before blood collection for clinical laboratory assessments and PK analysis.
- k. Site personnel will weigh the tubes to be dispensed and will record the weight of all tubes dispensed at each visit in the drug accountability logs. Site personnel will weigh the returned tubes (used and unused) and record the weight in the drug accountability logs. If a tube has been lost, discarded, or forgotten by the subject, then the site personnel will make a notation of this on the drug accountability logs.
- l. Subjects and/or caregivers will be instructed to apply study drug once daily at the approximate same time each day, based on subject and/or caregiver(s) preference.
- m. At all clinic visits, study drug will be applied after all safety and efficacy assessments have been conducted.
- n. The blood sample collected at Screening will serve as the pre-dose plasma concentration. PK sampling will occur on Day 1 at 1, 3, and 5 hours post-dose. A single PK sample will be collected on Day 28.
- o. The vIGA-AD™ assessment should be performed before the %BSA and EASI assessments.
- p. The subject's scalp should be excluded from the %BSA and EASI calculation.
- q. The LTS assessment should be conducted pre-dose.
- r. PP-NRS daily itch diaries will be dispensed at Day 1 (Baseline) and Day 8 and collected on Day 28.

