Appendix 4: Calculation of Percent Body Surface Area Affected and Eczema Area Severity Index

Calculation of %BSA Affected:

Note: At Screening, Baseline and for all efficacy assessments, lesions on the scalp will not be included in the calculation of %BSA affected as these areas will not be included in the efficacy analyses.

Measurement of involved BSA is estimated by the handprint method: the total palmar surface of the subject's palm and digits is approximately 1% of their total BSA.

Estimate the involved regional area by determining the number of "full" handprints plus the number of handprints covered if several smaller lesions are "pushed together."

For subjects ages 8 years and above the maximum involvement by region is as follows:

- Head and neck = 10% of overall BSA (10 handprints);
1 hand-sized lesion ~ 10% of head and neck area
- Arms/Upper extremities = 20% of overall BSA (20 handprints);
1 hand-sized lesion ~ 5% of the upper extremities
- Trunk (including axillae and groin) = 30% of overall BSA (30 handprints);
1 hand-sized lesion ~ 3.33% of the trunk
- Legs/Lower extremities (including buttocks) = 40% of overall BSA (40 handprints);
1 hand-sized lesion ~ 2.5% of the lower extremities

For subjects ages <8 years the maximum involvement by region is as follows:

- Head and neck = 20% of overall BSA (20 handprints);
1 hand-sized lesion ~ 5% of head and neck area
- Arms/Upper extremities = 20% of overall BSA (20 handprints);
1 hand-sized lesion ~ 5% of the upper extremities
- Trunk (including axillae and groin) = 30% of overall BSA (30 handprints);
1 hand-sized lesion ~ 3.33% of the trunk
- Legs/Lower extremities (including buttocks) = 30% of overall BSA (30 handprints);
1 hand-sized lesion ~ 3.33% of the lower extremities

Table 6. Calculation of Percent Body Surface Area Affected

Body Region	Number of Handprints for Each Region
Head and neck	
Arms/upper extremities	
Trunk	
Legs/lower extremities	
TOTAL Involved %BSA – sum of handprints for each region	

Note: Shaded cells will be calculated in the CRF.

%BSA = percent body surface area; CRF = case report form

Calculation of EASI score (scalp excluded)

Four anatomic sites – head, upper extremities, trunk, and lower extremities – are assessed for erythema, edema/papulation, excoriation and lichenification as seen on the day of the examination. The severity of each sign is assessed using a 4-point scale, half points may be used (e.g. 0.5, 1.5, 2.5):

- 0 = None (Absent)
- 1 = Mild

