12.3 Determination and Analysis of PK Parameters

Full precision concentration data and actual sample times will be used for the determination of all PK parameters.

Raw plasma concentrations for the derivation of pharmacokinetic parameters will be handled as described in Section 12.1.

The following PK parameters will be derived, based on available data:

- C_{max} (pg/mL) – maximum observed concentration
- T_{max} (hr) – time of the maximum observed concentration
- $C\tau$ (pg/mL) – last quantifiable concentration determined directly from individual concentration-time data
- T_{last} (hr) – time of the last quantifiable concentration
- AUC_{0-t} (pg•hr/mL) – area under the concentration-time curve from time zero to the last quantifiable concentration, calculated using a linear trapezoidal rule that includes summation from the time of the first measurable concentration to the time of the last measurable concentration as follows:

$$AUC_{0-t} = \sum_{i=1}^{n-1} \left[\frac{C_{i+1} + C_i}{2} (t_{i+1} - t_i) \right]$$

Where C_i is the i -th sample, t_i is the time of the i -th sample from dosing, and n is the number of available samples up to and including the final quantifiable concentration.

AUC values will be estimated using the linear-up, log-down method. A minimum of 3 data points are required for determination of an AUC.

The PK parameters as listed above will be obtained by non-compartmental analysis.

Individual PK parameters:

A raw data listing will be provided displaying the individual PK parameters. Results will be displayed using 3 significant digits.

Summary statistics of PK parameters:

Pharmacokinetic parameters (except T_{last} and $C\tau$) will be summarized using descriptive statistics (n , arithmetic mean, SD, CV % for the arithmetic mean, median, minimum, maximum, geometric mean, and CV % for the geometric mean). The geometric mean and CV % for the geometric mean will not be calculated for T_{max} . Results will be displayed using 3 significant digits.

Summary statistics of PK parameters will be determined by age group and overall. PK parameters of C_{max} and AUC_{0-t} will also be normalized to %BSA at Baseline by dividing each parameter by cm^2 of BSA of disease. For this calculation, 1% BSA is equal to 185 cm^2 .

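### Treated scalp is left out of the %BSA used to normalise Day 1 Cmax and AUC, which inflates the per-%BSA values of subjects who treat the scalp

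*Protocol*

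**What the plan says.** **Treatment of the scalp.** Protocol section 5.1.5 states: "Subjects are allowed, but not required, to treat scalp lesions with study drug". The protocol synopsis, protocol section 3.1 and SAP section 4 repeat this.

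**Measurement of %BSA.** Appendix 4 says that "lesions on the scalp will not be included in the calculation of %BSA affected", and the reason it gives is that the scalp is not part of the efficacy analyses. Footnote p of the Schedule of Assessments agrees: "The subject's scalp should be excluded from the %BSA and EASI calculation". The entry thresholds use the same scalp-excluded figure: at least 35% "of the BSA for subjects ages 2-11 years old", and at least 25% for ages 12-17.

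**Use in the PK analysis.** Under SAP section 12.3, Cmax and AUC0-t "will also be normalized to %BSA at Baseline by dividing each parameter by" the diseased area in cm², with the rule "For this calculation, 1% BSA is equal to 185" cm². SAP section 12.2 puts Baseline %BSA on the x-axis of two exposure figures and plots the normalised values in two more. Neither section mentions scalp.

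**Region sizes.** Appendix 4 gives "Head and neck = 20% of overall BSA (20 handprints") below age 8 and "Head and neck = 10% of overall BSA (10 handprints") from age 8.

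**The concern.** Leaving scalp out suits the efficacy endpoints. For PK, the same %BSA stands in for the area from which drug is absorbed, and there the omission matters. Drug taken up through a treated scalp adds to Cmax and AUC, but the scalp adds nothing to the denominator. The normalised value is therefore too high for a scalp user, and the same subject sits too far left on the two %BSA plots.

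Because scalp treatment is optional, the error differs from child to child. Two children of similar size and similar %BSA can differ in normalised exposure only because one treated the scalp. Appendix 4 gives head and neck twice the share below age 8, so for equal b and an equal scalp fraction the proportional error is twice as large there. The normalised parameters fall under a summary by age group, so the error could colour a comparison across ages.

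The protocol and SAP plan no record that would allow a correction:
- The Baseline visit list (protocol section 7.2) and the Schedule have no scalp item.
- The sensitive areas for local tolerability (section 6.3.5) do not include scalp.
- In-clinic doses, such as Day 1, are not entered in the diary (section 5.4).
- Tube weights include cream put on the scalp but cannot separate it.
- The lesion diagram in section 5.1.5 is optional.

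**Working it through.** **The plan's own constant.** 185 cm² × 100 = 18,500 cm² = 1.85 m² of total body surface, applied to every subject aged 2-17. The SAP gives no derivation, so the figure can be converted but not reproduced.

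**Inputs from the documents.** Head and neck share H = 20% under 8 and 10% from 8 (Appendix 4). Minimum scalp-excluded %BSA b = 35% for ages 2-11 and 25% for ages 12-17 (protocol section 4.2).

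**Assumptions not in the documents.** Scalp is a fraction f = 1/3 to 1/2 of head and neck. Absorption per cm² is the same on scalp as elsewhere.

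**Step 1: effect on the per-%BSA scale.** With exposure C, the plan reports C/b and the value per treated %BSA is C/(b + s). The ratio is (b + s)/b = 1 + s/b. The 185 cm² constant is common to all subjects and cancels.

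*Scalp affected in proportion to other skin.* If p = f × H is the scalp share of total BSA, then s/b = p/(100 − p).
- Under 8: 6.67/93.33 = 7.1% to 10/90 = 11.1%.
- From 8: 3.33/96.67 = 3.4% to 5/95 = 5.3%.

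*Whole scalp treated, b at the entry threshold.*
- Under 8: 6.67/35 = 19% to 10/35 = 29%.
- 8-11: 3.33/35 = 10% to 5/35 = 14%.
- 12-17: 3.33/25 = 13% to 5/25 = 20%.

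The effect shrinks as b rises. Under 8 at b = 60%, it is 6.67/60 = 11% to 10/60 = 17%.

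**Step 2: contrast between ages.** At the thresholds, with every child treating the whole scalp, the youngest are inflated relative to adolescents by 1.19/1.13 = 1.05 to 1.29/1.20 = 1.07. The order can reverse: setting 20f/b = 10f/25 gives b = 50, so a child under 8 with b above 50% has a smaller error than an adolescent at 25%. The step is at age 8 while the cohorts are 2-6, 7-11 and 12-17, so 7-year-olds in the middle cohort carry the 20% share.

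**Step 3: effect per cm².** With true total body surface T in m², the plan reports C/(185b), and exposure per treated cm² is C/[100T(b + s)]. Reported/true = (1 + s/b) × T/1.85. The ranges of T below are assumptions. The value of b is the entry threshold, and f = 1 (all of head and neck) is the hard upper bound.

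| Age | Assumed T (m²) | No scalp | f = 0.5 | f = 1 |
|---|---|---|---|---|
| under 8 | 0.5-0.9 | 0.27-0.49 | 0.35-0.63 | 0.42-0.76 |
| 8-11 | 0.8-1.4 | 0.43-0.76 | 0.49-0.86 | 0.56-0.97 |
| 12-17 | 1.2-1.9 | 0.65-1.03 | 0.78-1.23 | 0.91-1.44 |

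Break-even is T = 1.85/(1 + s/b). For a child under 8 at b = 35% it is 1.85/1.286 = 1.44 m² at f = 0.5 and 1.85/1.571 = 1.18 m² at f = 1. Below these sizes the reported per-cm² value is too low even with scalp treated.

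**Step 4: correcting scalp alone.** Adding scalp at f = 0.5 while keeping 185 cm² multiplies the value for an under-8 child by 35/45 = 0.78. That takes a value that is already too low further down.

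**The case against.** The strongest objection concerns direction. A reader might infer that area-normalised exposure is overstated, most of all in the youngest children. The documents do not support that for the per-cm² value the SAP reports. The same SAP paragraph fixes 1% BSA at 185 cm² for all ages, and in small children this outweighs the scalp effect: a child under 8 at 35% BSA would need a total surface above 1.18 m² to be overstated on balance, even if the whole head and neck were treated scalp. This part of the objection stands. It does not remove the scalp error, because the constant cancels in any per-%BSA comparison between subjects, the two %BSA plots do not use it, and it does nothing for the contrast between scalp users and non-users of similar size.

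Other parts also stand:
- The 19-29% range is near worst case, since it combines a fully treated scalp with the minimum body involvement. Drug goes on lesions, so the proportional figures are a fairer central reading.
- The primary PK endpoints are unnormalised and untouched. The normalised values are an added descriptive summary in cohorts of about 12, with no hypothesis test or decision rule attached.
- A reader might also infer that scalp treatment was never recorded and that the error cannot be repaired. The annotated CRF listed in SAP section 2 is not among the documents, and Day 1 dosing is supervised. What can be said is that the protocol and SAP specify no such record.

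**Conclusion.** The point holds in a limited form. The PK denominator comes from an efficacy measure that omits an area subjects may treat. In subjects who treat the scalp on Day 1, %BSA-normalised Cmax and AUC0-t are biased upward by (b + s)/b. A plausible size is about 7-11% under 8 and 3-5% from 8. The upper end is 19-29%, 10-14% and 13-20% for under 8, 8-11 and 12-17.

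These figures rest on the assumed scalp fraction and on equal absorption per cm². They apply to scalp users only, and the documents give no number for them. On the per-cm² scale, the assumed body sizes put the net bias downward in children under 8, and net overstatement appears only among larger adolescents. The matter bears on a secondary descriptive summary and its plots, in a study whose purpose is to measure systemic exposure. It is worth correcting because the change is small.

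**What to change.** 1. On Day 1, record whether scalp was treated and the number of treated scalp handprints.
2. In SAP sections 12.2 and 12.3, use total treated %BSA including scalp for the normalisation and for the %BSA plots.
3. In the same change, replace the 185 cm² constant with each subject's own total body surface, derived from the height and weight measured at Screening (protocol section 6.3.2) by a formula named in the SAP. Steps 2 and 3 belong together, because step 2 alone would worsen the per-cm² figure in the youngest.
4. Leave the efficacy %BSA and EASI as they are.

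If the Day 1 scalp area cannot be obtained, flag scalp users where source records allow, and label the metric as normalised to non-scalp BSA.

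The cost is one extra Baseline CRF item and a small derivation. Nothing here bears on whether the scalp should be treated.
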